## **12        QUALITY CONTROL AND QUALITY ASSURANCE**

Following a written DMID-accepted site quality management plan, each participating site(s) and its subcontractors are responsible for conducting routine quality assurance and quality control activities to internally monitor study progress and protocol compliance. The site principal investigator will provide direct access to all study-related sites, source data/data collection forms, and reports for the purpose of monitoring and auditing by the sponsor, and inspection by local and regulatory authorities. The site principal investigator will ensure all study personnel are appropriately trained and applicable documentations are maintained on site.

The SDCC will implement quality control procedures beginning with the data entry system and generate data quality control checks that will be run on the database. Any missing data or data anomalies will be communicated to the participating site(s) for clarification and resolution.

---

## 13 DATA HANDLING AND RECORD KEEPING

### 13.1 Data Management Responsibilities

The site principal investigator is responsible to ensure the accuracy, completeness, and timeliness of the data reported.

Data will be entered electronically over the Internet by site study staff into Advantage eClinical, developed and maintained by the SDCC. The eCRFs serve as the source documents for data collected. Paper case report forms derived from the eCRF are provided by the SDCC and are to be used only when Advantage eClinical is unavailable. Details on data handling procedures, procedures for data monitoring, and instructions for use of the system and completion of the eCRFs are provided in the study MOP, eCRF Instructions, and Advantage eClinical User's Guide.

The sponsor and/or its designee will provide guidance to the site principal investigators and other study personnel on making corrections to the eCRF.

### 13.2 Data Coordinating Center/Biostatistician Responsibilities

Data collection is the responsibility of the study personnel at the participating clinical study site under the supervision of the site principal investigator. During the study, the site principal investigator must maintain complete and accurate documentation for the study.

Emmes will serve as the SDCC for this study, and will be responsible for data management, quality review, analysis, and reporting of the study data.

### 13.3 Data Capture Methods

Clinical (including, but not limited to, AE/SAEs, concomitant medications, medical history, physical assessments, and clinical laboratory values) and reactogenicity will be entered into eCRFs via a 21 CFR Part 11-compliant internet data entry system provided by Emmes. The data system includes password protection and internal quality checks, such as automatic range checks, to identify data that appear inconsistent, incomplete, or inaccurate. Clinical data will be entered directly from the source documents.

Site staff who are delegated the responsibility by the study PI will be the data originators for clinical data entered directly into the eCRF. A list of all authorized data originators, including site staff, will be included on the Study Personnel/Signature Responsibility List.

---

### **13.4 Types of Data**

Data for this trial will include clinical, safety, and outcome measures (e.g., clinical laboratory values, reactogenicity, and immunogenicity data).

### **13.5 Study Records Retention**

Study records and reports including, but not limited to, eCRFs, source documents, ICFs, laboratory test results, and study drug disposition records will be retained for two years after a marketing application is approved for the study product for the indication for which it is being investigated; or, if no application is to be filed or if the application is not approved for the study product, until two years after the investigation is discontinued and the FDA has been notified. These documents will be retained for a longer period, however, if required by local regulations. ICFs for future use will be maintained as long as the sample/specimen exists.

No records will be destroyed without the written consent of the sponsor. It is the responsibility of the sponsor to inform the site principal investigator when these documents no longer need to be retained. The participating VTEU sites must contact DMID for authorization prior to the destruction of any study records.

---

## 14 CLINICAL MONITORING

Site monitoring is conducted to ensure that the human subjects' protections, study and laboratory procedures, study intervention administration, and data collection processes are of high quality and meet sponsor, ICH/GCP guidelines and applicable regulations, and that this trial is conducted in accordance with the protocol, protocol-specific MOP and applicable sponsor standard operating procedures. DMID, the sponsoring agency, or its designee will conduct site-monitoring visits as detailed in the clinical monitoring plan.

Site visits will be made at standard intervals as defined by DMID and may be made more frequently as directed by DMID. Monitoring visits will include, but are not limited to, review of regulatory files, accountability records, eCRFs, ICFs, medical and laboratory reports, and protocol and GCP compliance. Site monitors will have access to each participating site, study personnel, and all study documentation according to the DMID-approved site monitoring plan. Study monitors will meet with site principal investigators to discuss any problems and actions to be taken and will document site visit findings and discussions.

---

## 15 PUBLICATION POLICY

Following completion of the study, the lead PI is expected to publish the results of this research in a scientific journal. All investigators funded by the NIH must submit or have submitted for them to the National Library of Medicine's PubMed Central (<http://www.ncbi.nlm.nih.gov/pmc/>) an electronic version of their final, peer-reviewed manuscripts upon acceptance for publication, to be made publicly available no later than 12 months after the official date of publication. The NIH Public Access Policy ensures the public has access to the published results of NIH funded research. It requires investigators to submit final peer-reviewed journal manuscripts that arise from NIH funds to the digital archive PubMed Central upon acceptance for publication. Further, the policy stipulates that these papers must be accessible to the public on PubMed Central no later than 12 months after publication.

Refer to:

- NIH Public Access Policy, <http://publicaccess.nih.gov/>
- NIH Office of Extramural Research (OER) Grants and Funding, <http://grants.nih.gov/grants/oer.htm>

As of January 2018, all clinical trials supported by the NIH must be registered on ClinicalTrials.gov, no later than 21 days after the enrollment of the first subject. Results of all clinical trials supported by the NIH, generally, need to be submitted no later than 12 months following the primary completion date. A delay of up to 2 years is available for trials that meet certain criteria and have applied for certification of delayed posting.

As part of the result posting a copy of this protocol (and its amendments) and a copy of the Statistical Analysis Plan will be posted on ClinicalTrials.gov.

For this trial the responsible party is DMID which will register the trial and post results.

The responsible party does not plan to request certification of delayed posting.

Refer to:

- Public Law 110-85, Section 801, Clinical Trial Databases
- 42CFR11
- NIH NOT-OD-16-149

---

## **17 APPENDICES**

## Appendix A. Schedules of Events

**Table 7: Screening Visit Evaluations and Procedures.**

		Screen
Study day		-30 to -1
Study visit		00
Clinical Evaluations and Procedures	Tube	Screen
Sign consent form		X
Assessment of eligibility		X
Review medical history and con meds and collect demographic information		X
Complete physical exam and height and weight, calculate BMI		X
Vital signs (blood pressure, pulse, and oral temperature)		X
Provide HIV test counseling		X
Review of contraceptive/menstrual history; pregnancy avoidance counseling 		X
Pregnancy test (serum)  , creatinine, ALT, HIV-1/HIV-2 testing, anti-HCV antibody, HBsAg (mL)	SST	25.5
WBC, hemoglobin, platelets (mL)	EDTA	4
Blood Volume (mL)		29.5

For women of childbearing potential.

**Table 8: Schedule of Events and Study Procedures, Study Groups A, B, D, and E**

		Study Product Injection and Follow Up Visits												
Study day		1	2	4	8	29	32	36	57	60	64	85	181	422
Days after most recent vaccination		0	1	3	7	28	3	7	28	3	7	28	124	365
Visit Window (± number of days)		0	0	1	1	3	1	1	3	1	1	3	14	14
Study visit		01	02P	03	04	05	06	07	08	09	10	11	12	13P
Clinical Evaluations and Procedures	Tube													
Assessment of eligibility		X												
Assessment of individual halting criteria						X			X					
Review medical history and con meds 		X	X	X	X	X	X	X	X	X	X	X	X	X
Vital signs (blood pressure, pulse, and oral temperature  )		X		X	X	X	X	X	X	X	X	X 	X 	
Enrollment		X												
Study Product Injection		I-1				I-2			I-3					
Targeted physical exam		{X}		{X}	{X}	{X}	{X}	{X}	{X}	{X}	{X}	{X}	{X}	
Pre-administration reactogenicity assessment		X				X			X					
Evaluate study product injection site		X		X	X	X	X	X	X	X	X			
Provide and explain use of memory aid and thermometer		X				X			X					
Review memory aid			X	X	X		X	X		X	X			
Collection of solicited AEs		X	X	X	X	X	X	X	X	X	X			

		Study Product Injection and Follow Up Visits												
Study day		1	2	4	8	29	32	36	57	60	64	85	181	422
Days after most recent vaccination		0	1	3	7	28	3	7	28	3	7	28	124	365
Visit Window ( $\pm$ number of days)		0	0	1	1	3	1	1	3	1	1	3	14	14
Study visit		01	02P	03	04	05	06	07	08	09	10	11	12	13P
Clinical Evaluations and Procedures	Tube													
Collection of unsolicited AEs and SAEs 		X	X	X	X	X	X	X	X	X	X	X	X	X
Pregnancy test (urine) 		X				X			X					
WBC, hemoglobin, platelets (mL)	EDTA	3			3	3		3	3		3	3		
Creatinine, ALT 	SST	10			10	10		10	10		10	10		
Serum collection for antibody assays and secondary research (mL)	SST	8.5			8.5	8.5		8.5	8.5		8.5	8.5	8.5	
PBMC isolation for secondary research (mL)	NaHep/ACD 	60			60	60		60	60		60	34	60	
Whole blood collection for gene expression assays	PAXGene	2.5			2.5	2.5		2.5	2.5		2.5			
Total volume per visit (mL)		84			84	84		84	84		84	55.5	68.5	
Cumulative volume (prior 56 days)		113.5			197.5	281.5		365.5	420		420	391.5	68.5	

{ } required at this visit only if clinically indicated

P=phone assessment

0.5 mL of the designated study product will be injected IM in the deltoid muscle. Prior to the injection, a pre-administration reactogenicity assessment will be performed to establish baseline. After the injection, subjects will be observed for 30 minutes. The injection site will be evaluated and vital signs obtained during that period and before the subject leaves the clinic. Subjects will be provided with a Memory Aid and thermometer for recording daily maximum oral temperature, solicited injection site and systemic reactions, unsolicited AEs, and concomitant medications, beginning on the evening of the day of study product injection and continuing daily for the next seven days. Subjects will be encouraged to take their temperature around the same time each day and also if they feel feverish. Subjects will be instructed on how to use the memory aid and how to rate any AEs. Subjects will also be instructed to notify the study center if they develop any severe reactions and/or fever  $\geq 38^{\circ}\text{C}$  ( $100.4^{\circ}\text{F}$ ).

---

For women of childbearing potential. Must be confirmed as negative prior to injection of study product. The visit will also include review of contraceptive/menstrual history and pregnancy avoidance counseling.

After Study Visit 11 (or Study Day 85 if Study Visit 11 is not attended), through the end of study follow-up (Day 422), only SAEs, MAAEs, NOCMCs, and PIMMCs will be collected. Other unsolicited AEs and concomitant medications will not be collected.

Vital signs will be assessed only if clinically indicated.

Subjects must not eat or drink anything hot or cold, or smoke within 10 minutes prior to taking oral temperature.

 Blood collection volumes shown are the maximum that may potentially be drawn from the participant at each visit based on collection tube availability.

ACD collection tubes can be used to collect blood that will be processed for PBMC if appropriate NaHep tubes are unavailable.

**Table 9: Schedule of Events and Study Procedures, Study Group C.**

Study day		1	2	4	8	29	32	36	57	180	183	187	208	304	545
Days after most recent vaccination		0	1	3	7	28	3	7	28	151	3	7	28	124	365
Visit Window ( $\pm$ number of days)		0	0	1	1	3	1	1	3	7	1	1	3	14	14
Study visit		01	02P	03	04	05	06	07	08	09	10	11	12	13	14P
Clinical Evaluations and Procedures	Tube														
Assessment of eligibility		X													
Assessment of individual halting criteria						X				X					
Review medical history and con meds 		X	X	X	X	X	X	X	X	X	X	X	X	X	X
Vital signs (blood pressure, pulse, and oral temperature  )		X		X	X	X	X	X	X	X	X	X	X 	X 	
Enrollment		X													
Study Product Injection		I-1				I-2				I-3					
Targeted physical exam		{X}		{X}	{X}	{X}	{X}	{X}	{X}	{X}	{X}	{X}	{X}	{X}	
Pre-administration reactogenicity assessment		X				X				X					
Evaluate study product injection site		X		X	X	X	X	X		X	X	X			
Provide and explain use of memory aid and thermometer		X				X				X					
Review memory aid			X	X	X		X	X			X	X			
Collection of solicited AEs		X	X	X	X	X	X	X		X	X	X			

Study day		1	2	4	8	29	32	36	57	180	183	187	208	304	545
Days after most recent vaccination		0	1	3	7	28	3	7	28	151	3	7	28	124	365
Visit Window ( $\pm$ number of days)		0	0	1	1	3	1	1	3	7	1	1	3	14	14
Study visit		01	02P	03	04	05	06	07	08	09	10	11	12	13	14P
Clinical Evaluations and Procedures	Tube														
Collection of unsolicited AEs and SAEs 		X	X	X	X	X	X	X	X 	X	X	X	X	X	X
Pregnancy test (urine) 		X				X				X					
WBC, hemoglobin, platelets (mL)	EDTA	3			3	3		3	3	3	3	3	3	3	
Creatinine, ALT 	SST	10			10	10		10	10	10		10	10		
Serum collection for antibody assays and secondary research (mL)	SST	8.5			8.5	8.5		8.5	8.5	8.5		8.5	8.5	8.5	
PBMC isolation for secondary research (mL)	NaHep/ACD 	60			60	60		60	60	60		60	34	60	
Whole blood collection for gene expression assays	PAXGene	2.5			2.5	2.5		2.5		2.5		2.5			
Total volume per visit (mL)		84			84	84		84	84	84		84	55.5	68.5	
Cumulative volume (prior 56 days)		113.5			197.5	281.5		365.5	420	84		168	223.5	68.5	

{ } required at this visit only if clinically indicated

P=phone assessment

0.5 mL of the designated study product will be injected IM in the deltoid muscle. Prior to the injection, a pre-administration reactogenicity assessment will be performed to establish baseline. After the injection, subjects will be observed for 30 minutes. The injection site will be evaluated and vital signs obtained during that period and before the subject leaves the clinic. Subjects will be provided with a Memory Aid and thermometer for recording daily maximum oral temperature, solicited injection site and systemic reactions, unsolicited AEs, and concomitant medications.

---

beginning on the evening of the day of study product injection and continuing daily for the next seven days. Subjects will be encouraged to take their temperature around the same time each day and also if they feel feverish. Subjects will be instructed on how to use the memory aid and how to rate any AEs. Subjects will also be instructed to notify the study center if they develop any severe reactions and/or fever  $\geq 38^{\circ}\text{C}$  ( $100.4^{\circ}\text{F}$ ).

For women of childbearing potential. Must be confirmed as negative prior to injection of study product. The visit will also include review of contraceptive/menstrual history and pregnancy avoidance counseling.

After Study Visit 8 (or Study Day 57 if Study Visit 8 is not attended), through the time of the third study vaccination at Study Visit 09, only SAEs, MAAEs, NOCMCs, and PIMMCs will be collected. Other unsolicited AEs and concomitant medications will not be collected during this period. Collection of unsolicited AEs and concomitant medications will then resume at the time of the third vaccination and continue through Study Visit 12 (or Study Day 208 if Study Visit 12 is not attended), after which only SAEs, MAAEs, NOCMCs, and PIMMCs will be collected.

Vital signs will be assessed only if clinically indicated.

Subjects must not eat or drink anything hot or cold, or smoke within 10 minutes prior to taking oral temperature.

 Blood collection volumes shown are the maximum that may potentially be drawn from the participant at each visit based on collection tube availability.

ACD collection tubes can be used to collect blood that will be processed for PBMC if appropriate NaHep tubes are unavailable.

---

## Appendix B. List of Potentially Immune-Mediated Medical Conditions (PIMMCs)

### Gastrointestinal disorders

- Celiac disease (gluten-sensitive enteropathy)
- Inflammatory bowel disease (Crohn's disease, ulcerative colitis or proctitis)

### Liver disorders

- Autoimmune cholangitis
- Autoimmune hepatitis
- Primary biliary cirrhosis
- Primary sclerosing cholangitis

### Metabolic diseases

- Primary adrenal insufficiency (Addison's disease)
- Chronic lymphocytic thyroiditis (Hashimoto's disease) (Not exclusionary for enrollment)
- Diabetes mellitus type I
- Graves' or Basedow's disease

### Musculoskeletal disorders

- Antisynthetase syndrome
- Dermatomyositis
- Juvenile chronic arthritis/juvenile idiopathic arthritis (including juvenile Still's disease [macrophage activating syndrome])
- Mixed connective tissue disorder
- Polymyalgia rheumatica
- Polymyositis
- Psoriatic arthritis
- Relapsing polychondritis
- Rheumatoid arthritis
- Scleroderma, including diffuse systemic form and CREST syndrome

---

- Spondyloarthritis, including ankylosing spondylitis, reactive arthritis (Reiter's Syndrome) and undifferentiated spondyloarthritis
- Systemic lupus erythematosus
- Systemic sclerosis

## **Neuroinflammatory disorders**

- Acute disseminated encephalomyelitis, including site specific variants (e.g., non-infectious encephalitis, encephalomyelitis, myelitis, myeloradiculomyelitis)
- Possibly immune-mediated cranial nerve disorders (e.g., Bell's palsy)
- Guillain-Barré syndrome, including Miller Fisher syndrome and other variants
- Immune-mediated peripheral neuropathies and plexopathies, including chronic inflammatory demyelinating polyneuropathy, multifocal motor neuropathy and polyneuropathies associated with monoclonal gammopathy
- Multiple sclerosis
- Optic neuritis
- Transverse myelitis
- Myasthenia gravis, including Lambert-Eaton myasthenic syndrome (LEMS)

## **Skin disorders**

- Alopecia areata
- Autoimmune bullous skin diseases, including pemphigus, pemphigoid and dermatitis herpetiformis
- Cutaneous lupus erythematosus
- Erythema nodosum
- Localized scleroderma (morphea)
- Lichen planus
- Psoriasis (May not be exclusionary for enrollment, see [Section 5.1.2](#))
- Acute febrile neutrophilic dermatosis (Sweet's syndrome)
- Vitiligo (May not be exclusionary for enrollment, see [Section 5.1.2](#))

## **Vasculitides**

- Large artery vasculitis: Takayasu's arteritis and giant cell arteritis (temporal arteritis)
- Small and medium-sized artery vasculitis:

- Polyarteritis nodosa
- Mucocutaneous lymph node syndrome (Kawasaki disease)
- Microscopic polyangiitis
- Granulomatosis with polyangiitis (Wegener's granulomatosis)
- Eosinophilic granulomatosis with polyangiitis (Churg-Strauss syndrome)
- Thromboangiitis obliterans (Buerger's disease)
- Necrotizing vasculitis (systemic necrotizing vasculitis)
- Antineutrophil cytoplasmic antibody (ANCA)-associated vasculitis
- IgA vasculitis (Henoch-Schonlein purpura)
- Behcet's syndrome
- Leukocytoclastic vasculitis (hypersensitivity vasculitis)

## Others

- Antiphospholipid syndrome
- Autoimmune hemolytic anemia
- Autoimmune glomerulonephritis (including IgA nephropathy, glomerulonephritis rapidly progressive, membranous glomerulonephritis, membranoproliferative glomerulonephritis, and mesangioproliferative glomerulonephritis)
- Autoimmune myocarditis/cardiomyopathy
- Autoimmune thrombocytopenia
- Goodpasture syndrome
- Idiopathic pulmonary fibrosis
- Pernicious anemia
- Raynaud's phenomenon
- Sarcoidosis
- Sjögren's syndrome
- Stevens-Johnson syndrome
- Uveitis

## Appendix C. Toxicity Tables

Parameters for solicited AEs are reported in Table 3, Table 4, Table 5, and Table 6.

### Pulse and Blood Pressure

Physiologic Parameter	Mild (Grade 1)	Moderate (Grade 2)	Severe (Grade 3)
Tachycardia - beats per minute	101 - 115	116 - 130	> 130
Hypotension (systolic) mm Hg 	85 – 89	80 – 84	<80
Hypertension (systolic) mm Hg 	141 – 150	151 – 155	> 155
Hypertension (diastolic) mm Hg 	96 – 100	101 – 105	>105

The inclusion criteria for systolic blood pressure includes values from 85 through 150, inclusive and for diastolic blood pressure includes values  $\leq 100$ .

Subjects with baseline (prior to first vaccination) Grade 1 values of 85-89 mm Hg are defined with a hypotension (systolic) AE only due to post-vaccination values  $\leq 84$  mm Hg and the AE is Defined as Grade 1 based on values of 80 through 84 and Grade 2 based on values less than 80.

Subjects with baseline (prior to first vaccination) Grade 1 values of 141-150 mm Hg are defined with a hypertension (systolic) AE only due to post-vaccination values over 150 mm Hg and the AE is Defined as Grade 1 based on values of 151 through 155 mm Hg and Grade 2 based on values over 155.

Subjects with baseline (prior to first vaccination) Grade 1 values of 96-100 mm Hg are defined with a hypertension (diastolic) AE only due to post-vaccination values  $\geq 101$  mm Hg and the AE is Defined as Grade 1 based on values of 101 through 105 mm Hg and Grade 2 based on values over 105.

---

## Clinical Safety Laboratory Values

Hematology	Mild (Grade 1)	Moderate (Grade 2)	Severe (Grade 3)
WBC $10^3$ /UL (Decrease)	2.50 – 3.50	1.50 – 2.49	<1.50
WBC $10^3$ /UL (Increase)	13.01 – 15.00	15.01 – 20.00	>20.00
HgB g/dL (Decrease) (Female)	11.0 – 11.49	9.5 – 10.9	<9.5
HgB g/dL (Decrease) (Male)	12.0 – 12.5	10.0 – 11.9	<10.0
Platelets $10^3$ /UL (Decrease)	120 – 130	100 – 119	<100
Platelets $10^3$ /UL (Increase)	416 – 550	551 – 750	>750
Chemistry			
ALT IU/L (Increase)	47 – 105	106 – 175	>175
Creatinine mg/dL (Increase)	> ULN – 1.7	1.8 – 2.0	>2.0

ULN = upper limit of normal range

Clinical Adverse Events			
CARDIOVASCULAR	Mild (Grade 1)	Moderate (Grade 2)	Severe (Grade 3)
Arrhythmia		asymptomatic, transient signs, no Rx required	recurrent/persistent; symptomatic Rx required
Hemorrhage, Blood Loss	Estimated blood loss $\leq$ 100 mL	Estimated blood loss > 100 mL, no transfusion required	Transfusion required
RESPIRATORY			
	Mild (Grade 1)	Moderate (Grade 2)	Severe (Grade 3)
Cough	Transient- no treatment	Persistent cough;	Interferes with daily activities
Bronchospasm, Acute	transient; no treatment; 71% - 80% FEV1 of peak flow	requires treatment; normalizes with bronchodilator; FEV1 60% - 70% (of peak flow)	no normalization with bronchodilator; FEV1 <60% of peak flow
Dyspnea	Does not interfere with usual and social activities	Interferes with usual and social activities, no treatment	Prevents daily and usual social activity or requires treatment
GASTROINTESTINAL			
	Mild (Grade 1)	Moderate (Grade 2)	Severe (Grade 3)
Vomiting	No interference with activity or 1 - 2 episodes/24 hours	Some interference with activity or > 2 episodes/24 hours	Prevents daily activity or requires IV hydration

Diarrhea	2 - 3 loose or watery stools or < 400 gms/24 hours	4 - 5 loose or watery stools or 400 - 800 gms/24 hours	6 or more loose or watery stools or > 800gms/24 hours or requires IV hydration
SYSTEMIC REACTIONS	Mild (Grade 1)	Moderate (Grade 2)	Severe (Grade 3)
Allergic Reaction	pruritus without rash	localized urticaria	generalized urticaria; angioedema or anaphylaxis
All Other conditions	Mild (Grade 1)	Moderate (Grade 2)	Severe (Grade 3)
Illness or clinical adverse event (as defined according to applicable regulations)	No interference with activity	Some interference with activity not requiring medical intervention	Prevents daily activity and requires medical intervention

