### **8.1.1.1 Adverse Events Grading**

All AEs (laboratory and clinical symptoms) will be graded for severity and assessed for relationship to study product (see definitions). AEs characterized as intermittent require documentation of onset and duration of each episode. The start and stop date of each reported AE will be recorded on the appropriate eCRF.

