#### **Severity of Event:**

AEs will be assessed by the investigator using the protocol-defined grading system specified in [Section 8.1.2](#) and [Appendix C](#). For events not included in the protocol-defined grading system, the following guidelines will be used to quantify severity:

- Mild (Grade 1): Events that are usually transient and may require only minimal or no treatment or therapeutic intervention and generally do not interfere with the subject's usual activities of daily living.
- Moderate (Grade 2): Events that are usually alleviated with additional specific therapeutic intervention. The event interferes with usual activities of daily living, causing discomfort but poses no significant or permanent risk of harm to the research participant.
- Severe (Grade 3): Events interrupt usual activities of daily living, or significantly affects clinical status, or may require intensive therapeutic intervention. Severe events are usually incapacitating.

---

**Relationship to Study Product:** The assessment of the relationship of an AE to the administration of study product is made only by those with the training and authority to make a diagnosis and listed on the Form FDA 1572 as an investigator based on all available information at the time of the completion of the eCRF. Whether the AE is related or not, is not a factor in determining what is or is not reported in this trial. If there is any doubt as to whether a clinical observation is an AE, the event should be reported.

In a clinical trial, the study product must always be suspect. The relationship to study product will be assessed for AEs using the terms related or not related:

- Related – There is a reasonable possibility that the study product caused the AE. Reasonable possibility means that there is evidence to suggest a causal relationship between the study product and the AE.
- Not Related – There is not a reasonable possibility that the administration of the study product caused the event.

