### **8.6.3 Dose Escalation Halting Criteria**

Subjects are scheduled to receive three injections of the assigned study product, given on Days 1, 29, and 57 or on Days 1, 29, and 180. Dose escalation will proceed as described in the Protocol Summary. If one or more dose escalation stopping rules are met the SMC will be convened to review the safety information and determine whether dose escalation should proceed.

- Any subject develops a Grade 3 solicited or unsolicited systemic AE or a Grade 3 clinical laboratory AE that is judged related to the study product.
- Three or more subjects in the most recently enrolled study group develop the same Grade 3 solicited injection site AE related to the study product.
- Three or more subjects develop the same Grade 2 or higher solicited or unsolicited systemic AE or the same Grade 2 or higher clinical laboratory AE that is judged related to study product.
- Any subject has an event meeting an individual halting criterion.

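### The catch-all row of the Appendix C toxicity table leaves some unsolicited adverse events without a grade and keeps Grade 3 from an event that stops daily activity but needs no treatment

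*Protocol*

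**What the plan says.** Protocol 8.1.1.1 sets the duty: "All AEs (laboratory and clinical symptoms) will be graded for severity". Under Severity of Event it also sets an order. Investigators use Section 8.1.2 and Appendix C first; then, "For events not included in the protocol-defined grading system, the following guidelines will be used to quantify severity". That general scale defines Grade 2 partly by treatment, "Events that are usually alleviated with additional specific therapeutic intervention", together with interference with usual activities. Its Grade 3 lists alternatives: "Events interrupt usual activities of daily living, or significantly affects clinical status, or may require intensive therapeutic intervention".

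Appendix C closes with the All Other conditions row, which covers any illness or clinical AE. Grade 1 is the absence of interference, with intervention not mentioned. Grade 2 is "Some interference with activity not requiring medical intervention". Grade 3 is "Prevents daily activity and requires medical intervention".

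SAP Table 6 repeats this row in the same words. SAP 4.5.1 says unsolicited AEs are graded by SAP Tables 6 and 7, and the 8.1.1.1 scale is not carried into the SAP.

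Protocol 8.6.3 uses the grade of related events in two escalation criteria: "Any subject develops a Grade 3 solicited or unsolicited systemic AE or a Grade 3 clinical laboratory AE", and "Three or more subjects develop the same Grade 2 or higher solicited or unsolicited systemic AE".

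**The concern.** Grades in a catch-all row should cover every event sent to it. Here Grade 2 excludes events that need treatment, while Grade 3 demands both prevented activity and treatment, so events fall between them. The row's label claims every remaining condition. An investigator reading 8.1.1.1 literally could therefore conclude that the general scale is not available for these events, because they are already included in the table.

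The stake is one safety decision and some reporting. Under 8.6.3, a single related Grade 3 unsolicited systemic AE sends escalation to the Safety Monitoring Committee (SMC), whereas at Grade 2 it takes three subjects with the same AE. An ungraded event meets neither criterion. As a hypothetical case, take related dizziness, which is neither solicited nor named in Appendix C. It keeps one subject in bed for a day and needs no treatment. It is Grade 3 under 8.1.1.1 and cannot be Grade 3 under the row. The grade also feeds the severity rows of SAP Tables 18 and 48, and decides whether a non-serious event appears in SAP Table 55.

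**Working it through.** No stated power, sample size or error rate depends on this, so the check is an enumeration. Cross interference with activity (none, some, prevents) with need for medical intervention (no, yes): 3 × 2 = 6 combinations. Grade each by the Appendix C row, by the 8.1.1.1 scale, and by the row as reworded under the fix. The word interrupt in 8.1.1.1 is read as prevents, which is an assumption. A broader reading would add disagreement.

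| Interference | Intervention needed | Appendix C row | Protocol 8.1.1.1 | Reworded row |
|---|---|---|---|---|
| None | No | 1 | 1 | 1 |
| None | Yes | 1 | Unclear (3 if intensive) | 1 (3 if intensive) |
| Some | No | 2 | 2 | 2 |
| Some | Yes | No grade | 2 (3 if intensive) | 2 (3 if intensive) |
| Prevents | No | No grade | 3 | 3 |
| Prevents | Yes | 3 | 3 | 3 |

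1. Read literally, the row leaves 2 of 6 combinations without a grade and agrees with 8.1.1.1 on 3 of 6. On the remaining 1, the row gives Grade 1. There 8.1.1.1 is unclear because its Grade 1 speaks of minimal treatment and its Grade 2 joins specific treatment to interference.
2. If some is read as at least some, the combination of prevented activity and no intervention becomes Grade 2 in the row, against Grade 3 in 8.1.1.1. The ungraded count falls to 1 of 6. On neither reading is that combination Grade 3, and on neither reading is some interference with intervention graded.
3. The requirement for both conditions at Grade 3 is out of line with neighbouring rules. The dyspnea and vomiting rows of Appendix C join their Grade 3 conditions with *or*. Grade 3 for the solicited symptoms in Protocol Table 5 has no intervention condition.
4. The reworded row grades 6 of 6 and matches 8.1.1.1 on the 5 combinations where that scale is clear.

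The count depends on the two axes chosen. The documents give no frequency for such events, so no probability of an affected escalation decision is offered.

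**The case against.** The best reply is that the protocol already has a backstop. All AEs must be graded, and an event that meets no grade in the row can sensibly be treated as not included in the table. Protocol 8.1.1.1 then supplies the expected grade. That is reasonable practice, but the text does not say it, and a row labelled for all other conditions points the other way. Two careful investigators could reach different results.

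A reader might infer that the two scales give rival grades. On the literal reading they do not: the row is silent in the two problem combinations. A Grade 2 against Grade 3 clash needs the looser reading of some, which is unlikely, since the row and Table 5 both contrast some interference with prevented activity.

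A reader might also infer that escalation could pass a disabling event unchecked. The documents do not support that.

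- Escalation review uses data through at least seven days after the first injection, the same span as solicited collection. A reaction that stops activity may then also register as malaise, fatigue or headache, graded by Table 5.
- The fourth 8.6.3 criterion stops escalation on any individual halting criterion in 8.6.2.
- Under 8.6.1 the investigator may ask for a hold and an SMC meeting over any single event, and the sponsor may suspend dosing.
- No study halting rule in 8.6.1 turns on the grade of an unsolicited clinical AE.
- Every event is still counted in the any-severity row of SAP Table 48 and shown in SAP Listing 12.

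These points stand and keep the impact low. They are partial, however. The nearest 8.6.2 criterion speaks of a severe or sustained reaction, and severe is the Grade 3 label, so the ambiguity can carry over. The other routes rest on judgement.

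**Conclusion.** The row is wrong as written, with low practical impact. Two of six combinations are affected. Some interference that requires medical intervention has no grade, and prevented activity without intervention cannot be Grade 3. The general scale would give Grade 2 (3 if the intervention is intensive) and Grade 3, and the text does not clearly send these events there.

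The effect reaches only related unsolicited systemic AEs without their own row, under the one-subject Grade 3 and three-subject Grade 2-or-higher criteria of 8.6.3, plus the severity displays in SAP Tables 18, 48 and 55. Solicited reactions, laboratory values, vital signs and events with a named row are untouched. No missed trigger is shown. The conclusion rests on reading the row as worded and on taking interrupt in 8.1.1.1 to mean prevents.

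**What to change.** Reword the row in Appendix C and its copy in SAP Table 6, taking the highest grade that applies:

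- Grade 1: no interference with activity (unchanged).
- Grade 2: some interference, with or without medical intervention.
- Grade 3: prevents daily activity, or significantly affects clinical status, or requires intensive medical intervention.

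State that 8.1.1.1 applies to any event the tables do not grade.

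Replacing the row outright with the 8.1.1.1 definitions is a weaker choice. It may look neutral, but it changes the rule that governs these events now, and it leaves the case of no interference with treatment needed unclear.

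The cost is a wording amendment to the protocol and SAP, with IRB approval before implementation (Protocol 9.1). The SAP is at version 4.0 and describes some procedures in the past tense, so the grades of any such events already recorded should be checked, to avoid mixing two scales across groups. A few more events may reach Grade 2 or 3 and prompt SMC review. No study procedures are added.
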